#### Blood Sampling Volumes

During the Cohort 1 substudy, approximately 80 mL (or 200 mL, in case optional PBMC samples are taken) of blood will be drawn over a period of 1 year, which remains well below the limits of standard blood donation.

For details on the approximate blood sampling volumes collected by visit and the cumulative blood volumes in the Cohort 1 substudy, refer to the [Cohort 1 Substudy Time and Events Schedule](#).

Additional serum or urine pregnancy tests may be performed, as determined necessary by the investigator or required by local regulation, to establish the absence of pregnancy at any time during the subject's participation in the Cohort 1 substudy.

Repeat or unscheduled samples may be taken for safety reasons or for technical issues with the samples.

Subjects participating in the Cohort 1 substudy need to sign an additional ICF before the first substudy-related activity.

All male and female subjects participating in the Cohort 1 substudy, except for female subjects of non-childbearing potential, will be asked to use adequate birth control measures for sexual intercourse from at least 14 days before to at least 3 months after the third vaccination.

Before the third vaccination, a urine pregnancy test (for female subjects of childbearing potential), a targeted physical examination and measurements of vital signs will be performed. Subjects will have blood drawn for immunogenicity assessments as indicated in the [Cohort 1 Substudy Time and Events Schedule](#). Refer to Section 9.4 for further details on the immunogenicity evaluations. Physical examinations will be performed as indicated in the [Cohort 1 Substudy Time and Events Schedule](#).

Study vaccine will be prepared on-site by unblinded qualified study-site personnel not involved in any other study-related procedure who will place a blinding tape on the syringe to mask its content and send the vaccine to a blinded study vaccine administrator (see [Definitions of Terms](#)) for administration to the subject (see Section 14.3 for details). Refer to Section 6 for further details on dosage and administration and post-vaccination monitoring.

Adverse events, whether serious or non-serious, will be collected at all visits from the day of the third vaccination onwards until 28 days thereafter. Thereafter, reporting will be limited to all serious adverse events and IREs up to the subject's last study-related procedure. Solicited local and systemic adverse events (reactogenicity, see below) will be reported by the subject until 7 days after each administration of study vaccine. Adverse events will be followed by the investigator as specified in Section 12. Subjects will be instructed to contact the investigator before the next visit if they experience any adverse event or intercurrent illness that they perceive as relevant and/or can be possibly related to study vaccine in their opinion.

### **9.1.8. VAC52150 Vaccine Development Roll-over Study**

Female subjects who became pregnant with estimated conception within 28 days after vaccination with MVA-BN-Filo (or placebo) or within 3 months after vaccination with Ad26.ZEBOV (or placebo) and children born to vaccinated female subjects who became pregnant with estimated conception within 28 days after vaccination with MVA-BN-Filo (or placebo) or within 3 months after vaccination with Ad26.ZEBOV (or placebo) (unless local regulations have additional requirements for follow-up) will be eligible for enrollment into the VAC52150 Vaccine Development Roll-over study for long-term surveillance (for a total of up to 60 months after the prime vaccination). After unblinding, only female subjects and the children of female subjects enrolled in this study who received Ad26.ZEBOV and/or MVA-BN-Filo will remain in the VAC52150 Vaccine Development Roll-over study for long-term safety surveillance. After unblinding, female subjects and the children of female subjects who received placebo and have already been enrolled into the VAC52150 Vaccine Development Roll-over study will be discontinued from further participation in the roll-over study.

## **9.2. Endpoints**

Refer to Section 11.1 for an overview of safety and immunogenicity endpoints.

## 9.3. Safety Evaluations

### 9.3.1. Safety Assessments

The study will include the following evaluations of safety and tolerability as described below and according to the time points provided in the [Time and Events Schedule](#). Any clinically significant abnormalities occurring from signing of the ICF onwards until 42 days after the last vaccination (excluding third vaccination), and again from the day of the third vaccination until 28 days thereafter for subjects in the Cohort 1 substudy, must be recorded on the Adverse Event section of the CRF. Thereafter, reporting will be limited to all serious adverse events and IREs. Any clinically significant abnormalities (including those persisting at the end of the study/early withdrawal) will be followed by the investigator until resolution or until a clinically stable endpoint is reached (see Section 12). For reporting of IREs, refer to Section 12.3.3.

The investigators, together with the sponsor's medical monitor, will be responsible for the safety monitoring of the study, and will halt vaccination of further subjects in case any of the pre-specified pausing rules described in Section 9.3.2 have been met. Further safety measures with regards to vaccination are described in Sections 6.2 and 6.3.

An IDMC will be appointed by the sponsor formed with recommendations from the Clinical Steering Committee before the start of the study to perform regular review of the safety data during the study. Details regarding the IDMC are provided in Section 11.8.

### Adverse Events

All adverse events, whether serious or non-serious, will be collected at all visits from signing of the ICF onwards until 42 days after the last vaccination (excluding third vaccination), and again from the day of the third vaccination until 28 days thereafter for subjects in the Cohort 1 substudy. Thereafter, reporting will be limited to all serious adverse events and IREs up to the subject's last study-related procedure. Solicited local and systemic adverse events (reactogenicity, see below) will be reported by the subject until 7 days after each administration of study vaccine. Adverse events will be followed by the investigator as specified in Section 12.

### Solicited Adverse Events

Solicited adverse events (see [Definitions of Terms](#)) are precisely defined events that subjects are specifically asked about and which are noted by subjects in the diary. The subjects will be closely observed by study-site personnel for the first 30 ( $\pm 10$ ) minutes after each administration of study vaccine and again at 60 ( $\pm 15$ ) minutes after prime and boost vaccinations, and any unsolicited, solicited local or systemic adverse events will be documented during this period. Upon discharge from the site, subjects will receive a diary, a thermometer and a ruler to measure body temperature and solicited local reactions. Subjects will be instructed to record solicited local and systemic adverse events in the diary in the evening after each administration of study vaccine and then daily for the next 7 days (until the 7-day post-vaccination visits) at approximately the same time each day to serve as a reminder to the subject for the next visit. On the 7-day post-vaccination visits, the diary needs to be completed on site before the subject leaves the site. The investigator should discuss the information from the diary with the subject,

document the relevant information in the clinic chart, and complete the relevant parts of the CRF as described in the CRF Completion Guidelines.

On-site and diary reported solicited adverse events will be captured on a separate CRF page as described in the CRF Completion Guidelines, in contrast to the unsolicited adverse events which will be reported on the Adverse Event page of the CRF. The investigator must record in the CRF his/her opinion concerning the relationship of the adverse event to study vaccine.

### ***Solicited Local (Injection Site) Adverse Events***

Subjects will also be instructed on how to note occurrences of erythema, induration/swelling (measured using the ruler supplied), pain/tenderness and itching at the injection site in the evening after each administration of study vaccine and then daily for the next 7 days in the diary at approximately the same time each day.

### ***Solicited Systemic Adverse Events***

Subjects will be instructed on how to record daily body temperature using a thermometer provided for home use. Subjects should record the body temperature in the evening after each vaccination and then daily for the next 7 days in the diary. Body temperature should be measured at approximately the same time each day. If more than one measurement is made on any given day, the highest value will be recorded in the CRF.

Subjects will also be instructed on how to note the following symptoms in the evening after each administration of study vaccine and then daily for the next 7 days in the diary at approximately the same time each day:

- Nausea/vomiting
- Headache
- Myalgia
- Arthralgia
- Fatigue/malaise
- Chills
- Fever

If a ***solicited local or systemic adverse event*** is not resolved the 7-day post-vaccination visit, the follow-up will be captured on the diary. The subject will be instructed to record the date of last symptoms and maximum severity in the diary after resolution.

### **Cardiac Events**

In case any cardiac sign or symptom develops after the boost vaccination, the subject should be referred to a local cardiologist where the appropriate work-up which might include an ECG and/or troponin I assessments, if available, should be performed.

### **Clinical Laboratory Tests**

Blood samples for serum chemistry and hematology, and for other tests (see below) and a urine sample for urinalysis will be collected at the time points indicated in the **Time and Events Schedule**. The investigator must review the laboratory results, document this review, and record any clinically relevant changes occurring during the study in the Adverse Event section of the CRF until 42 days after the last vaccination (excluding third vaccination), and again from the day

of the third vaccination until 28 days thereafter for subjects in the Cohort 1 substudy. Thereafter, only serious adverse events and IREs need to be recorded. The laboratory reports must be filed with the source documents. For reporting of IREs, refer to Section [12.3.3](#).

Approximate blood volume expected to be drawn per visit for clinical laboratory assessments:

- 10 mL for Cohorts 1, 2a and 2b. Note: in Cohort 2a (HIV-infected subjects), an additional 2 mL will be taken for monitoring of CD4+ cell count at screening, on Day 1, on the day of the boost vaccination and 42 days after the boost vaccination.
- 6 mL at screening and 4 mL at other visits for Cohort 3 (4 to 11 years of age). These blood volumes are approximate and the site should follow their own Standard Operating Procedures for phlebotomy in children.

The following tests will be performed by the local laboratory, unless otherwise specified:

- Hematology Panel
  - hemoglobin
  - hematocrit
  - red blood cell count
  - white blood cell count with differential
  - platelet count
- Serum Chemistry Panel
  - sodium
  - potassium
  - blood urea nitrogen
  - aspartate aminotransferase
  - alanine aminotransferase
  - total bilirubin
  - creatinine
  - FSH (in women >45 years of age with amenorrhea for less than 2 years or ≤45 years of age with amenorrhea for more than 6 months)
- Urinalysis – Dipstick
  - specific gravity
  - pH
  - glucose
  - protein
  - blood
  - ketones

In case of positive urinalysis dipstick results for >1+ protein or blood, the sediment will be examined microscopically (only RBC will be documented).

Additional clinical laboratory assessments to be performed are as follows:

- Serum pregnancy test for female subjects of childbearing potential at screening;
- Urine pregnancy test for female subjects of childbearing potential before each study vaccination;
- CD4+ cell count for HIV-infected subjects (Cohort 2a) at screening, on Day 1, on the day of the boost vaccination and at 42 days after the boost vaccination;
- Serology: HIV type 1 and type 2.

Laboratory values will be determined according to the Toxicity Table for Use in Trials Enrolling Healthy Adults ([Attachment 2](#)) or the Toxicity Table for Use in Trials Enrolling Children Greater Than 3 Months of Age ([Attachment 3](#)).

### **Electrocardiogram**

A single, 12-lead ECG will be performed for subjects  $\geq 18$  years of age at screening and interpreted locally. Additional ECG monitoring may be performed at other time points if clinically indicated. During the collection of ECGs, subjects should be in a quiet setting without distractions (eg, television, cell phones). Subjects should rest in a supine position for at least 5 minutes before ECG collection and should refrain from talking or moving arms or legs. If blood sampling or vital sign measurement is scheduled at the same time point as ECG recording, the procedures should be performed in the following order: vital signs, ECG, blood draw.

### **Vital Signs (blood pressure, pulse/heart rate, body temperature)**

Vital sign measurements will be performed at the time points indicated in the [Time and Events Schedule](#). Blood pressure and pulse/heart rate measurements will be assessed (at rest) with a completely automated device. Manual techniques will be used only if an automated device is not available. Confirmatory measurements can be performed if inconsistent with a prior measurement.

Body temperature is preferably measured axillary. If the body temperature was measured at another site this needs to be captured in the CRF.

### **Physical Examination**

A full physical examination including height and body weight will be performed at screening. Calculation of the body mass index (BMI; Cohorts 1 and 2) or growth percentiles according to CDC growth charts (Cohort 3; see Section [4.2.3](#)), will be recorded in the CRF. At other visits, an abbreviated, symptom-directed physical examination will be performed as indicated based on any clinically relevant issues, clinically relevant symptoms and medical history. The symptom-directed physical examination may be repeated if deemed necessary by the investigator. Physical examinations will be performed by the investigator or by a designated medically-trained clinician.

A full physical examination includes the following: general appearance, eyes, ears, nose, throat, cardiovascular system, respiratory system, gastrointestinal system, and skin and mucous

membranes. A genitourinary exam is not required. A neurological and musculoskeletal examination as well as an examination of the lymph nodes will also be performed. An abbreviated, symptom-directed physical examination includes examination of the injection site(s), heart, lungs and abdomen.

The height should be measured barefooted at the screening visit. To obtain the actual body weight, subjects must be weighed lightly clothed.

### **9.3.2. Pausing Rules**

The investigators and the sponsor's medical monitor will review the safety of enrolled subjects on an ongoing basis. The sponsor's medical monitor will be involved in all discussions and decisions. These pausing rules are not applicable for the third vaccination.

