  - The investigator or the designee will document unsolicited adverse events from signing of the informed consent form (ICF)/assent onwards until 42 days post-last vaccination (excluding the third vaccination), and again from the day of the third vaccination until 28 days thereafter for subjects in the Cohort 1 substudy (note: events that started before the third vaccination but are still present at the time of third vaccination should also be recorded). The investigator or the designee will document serious adverse events and immediate reportable events (IREs) from signing of the ICF/assent onwards until the end of the study.
  - Safety measures, including an electrocardiogram (ECG; for subjects  $\geq 18$  years, performed at screening), physical examinations, vital sign measurements, clinical laboratory and pregnancy testing, will be performed at scheduled visits during the study, which lasts up to 1 year after the prime vaccination in subjects who received Ad26.ZEBOV or MVA-BN-Filo.

- Any clinically significant abnormalities (including those persisting at the end of the study/early withdrawal) will be followed by the investigator until resolution or until a clinically stable endpoint is reached.
- Several safety measures are included in this protocol to minimize the potential risk to subjects, including the following:
  - The neuroinflammatory disorders listed in Section 12.1.1 should be categorized as IREs and should be reported to the sponsor as described in Section 12.3.3.
  - There are pre-specified pausing rules that would result in pausing of further vaccination if predefined conditions occur, preventing exposure of new subjects to study vaccine until an Independent Data Monitoring Committee (IDMC) reviews all safety data (see Section 9.3.2).
  - Subjects will discontinue study vaccine for the reasons included in Section 10.2.
  - If acute illness (excluding minor illnesses such as diarrhea or mild upper respiratory tract infection) or fever (body temperature  $\geq 38.0$  °C) occur at the scheduled time for vaccination, the subject may be vaccinated up to 10 days beyond the window allowed for the scheduled vaccination, or be withdrawn from that vaccination at the discretion of the investigator and after consultation with the sponsor (see Section 6.2).
  - Contraindications to boost and third vaccinations are included in Section 6.3.

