#### **Secondary Objectives**

The secondary objectives are:

- To assess humoral immune responses, as measured by ELISA, to the EBOV GP at 21 days post boost of different vaccination schedules of Ad26.ZEBOV and MVA-BN-Filo administered IM as heterologous prime-boost regimens on Days 1 and 29, Days 1 and 57, or Days 1 and 85, in healthy adults, including elderly subjects, and on Days 1 and 29 and Days 1 and 57 in HIV-infected subjects and healthy children in 2 age strata.
- To assess the safety and tolerability of a third vaccination with Ad26.ZEBOV administered at least 1 year post prime in a subset of approximately 90 healthy adults, including elderly subjects, in Cohort 1 (Groups 1 and 2).

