## 6.3. Contraindications to Boost and Third Vaccinations

A subject will not be given the boost or third vaccination if he or she experiences any of the following events at any time after the prime or boost vaccination, respectively:

1. Anaphylaxis clearly attributable to vaccination with study vaccine; *OR*
2. Generalized urticaria within 72 hours of vaccination considered to be at least possibly related to study vaccine; *OR*
3. A serious adverse event considered to be at least possibly related to study vaccine; *OR*
4. Injection site ulceration, abscess or necrosis considered to be at least possibly related to the study vaccine; *OR*
5. Any other safety concern threatening the subject's safety or persisting clinically significant abnormality considered to be related to prime vaccination.

Subjects experiencing any of the events described above must not receive any further study vaccine, but should be monitored for safety and for immunogenicity according to the protocol as described in Section 10.2.

An ad hoc IDMC meeting may be requested via the sponsor for any single event or combination of multiple events which are considered to jeopardize the safety of the subjects.

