#### **Any cohort**

If any of the following events occur in any subject in any cohort who received at least one dose of study vaccine in the study (at any site), the site investigator will halt the vaccination of further subjects in all cohorts and the sponsor's medical monitor will be notified immediately. The sponsor's medical monitor will inform all the other investigators to halt further vaccination as well.

- Death in any subject, considered at least possibly related to the study vaccine; *OR*
- An anaphylactic reaction within 24 hours of vaccination or the presence of generalized urticaria within 72 hours of vaccination in any subject, considered at least possibly related to the study vaccine; *OR*
- A life-threatening or other serious adverse event in any subject, considered at least possibly related to the study vaccine.

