#### **Cohorts 1, 2 and 3**

If any of the following events occur in any subject from Cohorts 1, 2 or 3 who received at least one dose of study vaccine in the study (across all sites), the sponsor's medical monitor will notify all investigators to halt vaccination of further subjects:

- Three or more subjects experience a severe (grade 3) (non-serious) unsolicited adverse event (of the same type) considered to be related to any of the study vaccines that persists for 3 or more days; *OR*
- Three or more subjects experience a persistent (upon repeat testing) severe (grade 3) (non-serious) abnormality (including unexplained hematuria) related to the same laboratory parameter and considered to be related to any of the study vaccines; *OR*
- Three or more subjects experience the same severe (grade 3) (non-serious) solicited systemic reaction considered to be related to any of the study vaccines that persists for 3 or more days (subjective systemic reaction corroborated by study personnel).

In case of occurrence of any of the events described above, the sponsor's medical monitor will notify the IDMC immediately. Dosing will be halted and health authorities will be notified. Within 3 business days, the IDMC will convene to review the available safety data as outlined in the charter and to discuss study suspension or discontinuation of further vaccination or to decide that vaccination may resume. The sites will be allowed to resume activities upon receipt of a written notification from the sponsor. The criteria for pausing will be re-set each time and the same criteria have to be met again to halt further vaccination.

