## **11.8. Independent Data Monitoring Committee**

An IDMC will be established to monitor data on an ongoing basis to ensure the continuing safety of the subjects enrolled in this study. The committee will meet periodically to review interim data. Ad hoc IDMC meetings may be requested via the sponsor for any single event or combination of multiple events which are considered to jeopardize the safety of the subjects. After the review, the IDMC will make recommendations regarding the continuation of the study. The details will be provided in a separate IDMC charter.

The IDMC will be appointed by the sponsor with recommendations from the Clinical Steering Committee (see Section 11.9) before the start of the study. The IDMC will consist of at least one medical expert in the relevant therapeutic area and at least one statistician. The IDMC responsibilities, authorities, and procedures will be documented in its charter. Any safety reports/interim data from the cohorts in this study reviewed by the IDMC and the recommendations of the IDMC will be shared with the local health authorities and the IECs/IRBs.

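### The third vaccination is exempt from every pausing rule, and no binding substitute obliges anyone to stop third doses in other subjects after a related serious event

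*Protocol*

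**What the plan says.** Protocol Section 9.3.2 has two sets of pausing rules.

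- **Single-event triggers, all cohorts.** These open: "If any of the following events occur in any subject in any cohort who received at least one dose of study vaccine". They cover a related death, a related anaphylactic reaction (within 24 hours) or generalized urticaria (within 72 hours), and a related life-threatening or other serious adverse event. One such event stops vaccination of further subjects in all cohorts.
- **Count triggers, Cohorts 1 to 3.** These need three or more subjects with the same kind of related grade 3 finding.

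The section closes with immediate IDMC notification and a deadline: "Within 3 business days, the IDMC will convene to review the available safety data as outlined in the charter".

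The opening paragraph of 9.3.2 ends with the exemption: "These pausing rules are not applicable for the third vaccination". Amendment 3, which introduced the third dose, lists 9.3.2 among the sections changed for the substudy but does not explain the exemption.

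Third-dose safety is itself a secondary objective in Section 2.1: "To assess the safety and tolerability of a third vaccination with Ad26.ZEBOV administered at least 1 year post prime".

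**The concern.** The third dose is Ad26.ZEBOV at the same dose as the prime. As a prime it stays under the single-event triggers; as a third dose it does not. Familiarity with the product therefore does not explain the difference, and no other reason is offered.

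At stake is a compulsory stop. For prime and boost, one qualifying event stops dosing until an independent committee has looked. For dose 3, the next subject may be dosed unless someone chooses to intervene, in a substudy set up partly to learn whether a third dose is safe.

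**Working it through.** **Step 1. What the exemption can mean.** It has two readings.

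- (a) Events after dose 3 trigger nothing.
- (b) Third doses are not held when a pause is triggered. The single-event paragraph covers anyone who has had at least one dose, so a dose-3 event would still stop prime and boost.

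On either reading, third doses themselves are under no mandatory halt.

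**Step 2. Is there a binding substitute elsewhere?**

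| Provision | What it does | Obliges a stop of third doses in others? |
|---|---|---|
| Halt duty in Synopsis (Safety Evaluations), 3.1 and 9.3.1 | "will halt vaccination of further subjects in case any of the pre-specified pausing rules described in Section 9.3.2 have been met" (9.3.1) | No; it depends on a 9.3.2 rule being met |
| 6.3 Contraindications | Bars a subject who "experiences any of the following events at any time after the prime or boost vaccination, respectively" | No; it binds only the affected subject, on events before dose 3 |
| 10.2 Discontinuation | Per-subject decision | No |
| 9.1.7 Substudy procedures | Visits, blood volumes, contraception, event collection | No halt criterion |
| 6.3 and 11.8, ad hoc IDMC | "Ad hoc IDMC meetings may be requested via the sponsor for any single event or combination of multiple events" (11.8) | No; optional, with no deadline and no hold meanwhile |
| 11.8, periodic IDMC review | Recommendations on continuing | No dose-3 criterion |
| 9.3.2, ongoing medical review | Duty to review | No duty to stop |
| 12.1.1, 12.3.1, 12.3.2 (SAE, IRE, SUSAR reporting) | Duty to report | No |
| 17.1 and 17.9.2 | Immediate-hazard changes; sponsor may terminate | Powers, not duties |
| SAP Attachment 2 | Says lasting related solicited events lead to a pause | Restates a protocol rule; adds nothing for dose 3 |

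No row supplies the obligation. The charter cited in the SAP reference list is dated September 2016, before Amendment 3 (4 May 2017). A later revision with a dose-3 rule cannot be excluded, but neither document mentions one.

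**Step 3. Illustrative size.** The plan states no figure for this point. Its Table 9 uses P(at least one event) = 1 − (1 − p)^n, which reproduces: n = 55 at 1% gives 42%; n = 110 at 1% gives 67%; n = 880 at 0.1% gives 59%.

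Active third doses, assuming the 5:1 allocation of Section 3.1 carries over: 90 × 5/6 = 75 (binomial 95% range 68 to 82).

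| Assumed true rate | n = 68 | n = 75 | n = 82 |
|---|---|---|---|
| 0.1% | 6.6% | 7.2% | 7.9% |
| 0.5% | 28.9% | 31.3% | 33.7% |
| 1% | 49.5% | 52.9% | 56.1% |
| 2% | 74.7% | 78.0% | 80.9% |

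The top of the range is set loosely. Section 1.1.2.1 reports no vaccine-related serious adverse events in three studies of a prototype Ad26 vaccine given to more than 200 subjects. The one-sided 97.5% upper limit with zero events is 1 − 0.025^(1/n), which is 1.8% at n = 200.

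**Step 4. What a pause would defer.** Active doses deferred = 75 / (months × 30.4) × days of pause. Three business days is taken as 3 to 5 calendar days; even dosing is assumed.

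- Over 3 months (the 12-to-15-month window in Table 6): 2.5 to 4.1 doses.
- Over 6 months: 1.2 to 2.1.
- Over 1 month: 7.4 to 12.3.

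**The case against.** **Other safeguards remain.** Serious and immediate reportable events must reach the sponsor within 24 hours, unexpected related ones go to authorities and ethics committees, the medical monitor reviews continuously, and an IDMC meeting can be called. The sponsor has used its discretion before: it halted all vaccinations after a Miller Fisher case in another study. This stands. A reader might infer that third-dose recipients have no protection at all; the documents do not support that. What is missing is a binding rule to stop.

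**Section 1.2.5 is not contradicted.** It credits the pausing rules with "preventing exposure of new subjects to study vaccine until an Independent Data Monitoring Committee (IDMC) reviews all safety data". A reader might infer that the exemption breaks this promise. But substudy subjects have already had prime and boost, so they are not clearly new subjects. The section lists the rules without mentioning the exemption, which falls short of a contradiction.

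**The expected risk is low and the benefit small.** Subjects have tolerated the same product at the same dose, and 6.3 screens out those with earlier related events. A Phase 1 study gave this third dose at one year, although Section 3.2 reports only its antibody results, not how many were dosed or their safety. Multiplying Steps 3 and 4 (three-month spread), the expected number of doses deferred is about 0.2 to 0.3 at a 0.1% rate, 0.8 to 1.3 at 0.5%, and at most 3.2 at 2%. This too stands. But a pause matters less for the few doses deferred than for requiring review before dosing resumes.

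**The exemption was deliberate.** It was, in that Amendment 3 revised 9.3.2 for the substudy. No rationale accompanies it.

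**Conclusion.** The point holds in this form: Section 9.3.2 removes every pausing rule for the third vaccination, and neither the protocol nor the SAP puts a binding rule in its place. After a related death, anaphylaxis or generalized urticaria, or serious adverse event following dose 3, stopping third doses in other subjects is discretionary.

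This rests on the text, not on any calculation. The probabilities depend on assumed event rates, on 5:1 carrying over and on roughly 90 participants; they do not show that a third dose is hazardous, and a reader should not infer that. Two limits apply: the IDMC charter was not available, and the judgement is of the protocol at Amendment 3 (the 2018 SAP describes third doses as already given). It is a cheap improvement to patient protection and puts no planned analysis in doubt.

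**What to change.** Replace the exemption sentence in 9.3.2 with:

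> *The 'Any cohort' triggers also apply to events after the third vaccination: if one is met, further third vaccinations are halted, the IDMC is notified immediately and convenes within 3 business days, and third vaccinations resume only after its review. The 'three or more subjects' triggers do not apply to the third vaccination.*

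Leave the 'Any cohort' paragraph unchanged for prime and boost. On reading (b) it already stops them after a dose-3 event, and no existing mandatory halt should be lost.

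Add a note to Table 6 allowing third doses delayed by such a pause to be given after 15 months, with the delay recorded. SAP Section 2.3 already contrasts third doses given within and beyond 30 days after Day 365. Align the IDMC charter.

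The wording is short, but it is a protocol amendment and needs ethics and regulatory submission. The operational cost is a brief delay of a few third doses, as in Step 4. On reading (a), a pause of prime and boost after a dose-3 event would be new; boosts pushed beyond their ±3-day window would leave the SAP per protocol set.
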